### **3. Methods and Materials**

#### **3.1. Study population**

The study population of this proposed clinical trial is adults aged 60 years and above living in residential care homes or attending long-term care facilities in Hong Kong. The subject inclusion criteria are:

1. have at least 6 teeth which are not indicated for extraction, and
2. have basic self-care ability.

Adults with one or more of the following conditions will be excluded:

1. have serious debilitating health/medical conditions, and
2. have cognitive problems or major problems in communication.

About 10 residential care homes or long-term care institutions served by NGO dental outreach teams in various districts with different background, such as private or publicly funded homes, will be selected by the PI in consultation with the NGOs. All elders living in the selected residential homes will be invited to attend a free dental examination. Elders fulfilling the inclusion criteria will be invited to participate in this study and informed written consent will be obtained before commencement of the study. Dental treatments other than the study interventions will be provided by dentists from the NGOs which serve the residential homes.

#### **3.2. Sample size**

This non-inferiority trial aims to compare the caries preventive effect of applications of 38% SDF solution and that of combined 10% povidone iodine solution and 5% NaF varnish. A non-inferiority margin of 0.8 surface for the difference in the mean number of new caries surfaces over the 24-month study period is considered not clinically significant. The estimated sample size is based on the lower limit of the 2-sided 95% confidence interval for the difference set above the non-inferiority margin and the statistical power of the study being set at 90% ( $\beta=0.10$ ). The estimated standard deviation is 2.0, based on the results of a previous clinical trial conducted in Hong Kong (Tan et al., 2010). Using the statistical power analyses software, G\*Power (version 3.1.7; Franz Faul, Universität Kiel, Kiel, Germany), the total required number of elders in each group is calculated to be 133. Allowing for a drop-out rate of 20% in this 24-month study, an initial sample size of 166 subjects in each group or a total of 332 subjects is needed.

With a total sample size of 332 subjects and an estimated mean number of one untreated early/shallow root caries lesions per subject (Department of Health, 2013), there will be 332 root caries lesions in total or 166 lesions in each study group for caries arrest treatment. With this sample size, there is approximately 85% power that an absolute 15% difference in dental caries arrest rates between two groups can be shown to be statistically significant at the 5% level using Chi-square test when the overall success rate of the caries arrest treatment is around 80%.

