### **Null hypotheses to be tested:**

1. In this non-inferiority randomised controlled trial, the primary hypothesis to be tested is that 4-monthly application of 10% povidone iodine solution and 5% sodium fluoride varnish is at least not appreciably worse than a 38% SDF solution in preventing new dental root caries development over a 24-month period. The primary outcome measure is the development of new root surface caries lesions in the teeth of the elders.
2. The secondary hypothesis to be tested is that 4-monthly application of 10% povidone iodine solution and 5% sodium fluoride varnish is at least not appreciably worse than a 38% SDF solution in arresting active root caries over a 24-month period. The secondary outcome measure is the conversion of active (soft/demineralized) root surface caries lesions to inactive (hard/remineralized) lesions.

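### The non-inferiority criterion in section 3.2 is wrong as printed: the order of subtraction and the sign of the 0.8 margin are undefined, and with +0.8 the lower limit cannot show non-inferiority in either order

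*Protocol*

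**What the plan says.** The primary hypothesis (protocol, section 2, under the null hypotheses) is that the povidone iodine/varnish regimen "is at least not appreciably worse than a 38% SDF solution in preventing new dental root caries development over a 24-month period". On the endpoint it says: "The primary outcome measure is the development of new root surface caries lesions in the teeth of the elders". This is a count of harm, so a higher value is worse.

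Section 3.2 then gives "A non-inferiority margin of 0.8 surface for the difference in the mean number of new caries surfaces over the 24-month study period", and bases the sample size on the "lower limit of the 2-sided 95% confidence interval for the difference set above the non-inferiority margin", with 90% power and SD 2.0. It reports that "the total required number of elders in each group is calculated to be 133", raised to 166 per group (332 in total) for 20% drop-out.

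No section says whether the difference is test minus SDF or SDF minus test, and the margin carries no sign. Section 3.5 plans a two-sample t-test for a difference between the groups, by intention to treat and per protocol. It mentions no margin, confidence limit or direction.

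**The concern.** For a harmful count with the difference taken as test minus control, which is the usual order, non-inferiority is shown when the upper confidence limit lies below a positive margin. Section 3.2 names the lower limit and asks for it to lie above a margin printed as 0.8. Taken at face value, that sentence cannot support the primary hypothesis.

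An analyst or report writer who works from the protocol has no other non-inferiority criterion to turn to. They would have to choose the order of subtraction and the sign themselves. Of the four possible combinations, only one gives a valid rule.

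**Working it through.** **Inputs.** Margin 0.8, SD 2.0, 95% two-sided interval (one-sided 0.025), power 90%, 133 per group: all from section 3.2. True difference of zero for planning: an assumption, since the protocol does not state it; other values are tabulated below.

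**Step 1: reproduce the stated sample size.** Normal approximation:

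n = 2 × SD² × (1.96 + 1.2816)² / 0.8² = 2 × 4 × 10.51 / 0.64 = 131.3, so 132 per group.

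The noncentral-t calculation gives power 0.8993 at 132 and 0.9015 at 133, so 133 is reproduced. Drop-out: 133 / 0.80 = 166.25, stated as 166.

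**Step 2: precision.** SE = 2.0 × √(2/133) = 0.245. Half-width of the 95% interval = 1.96 × 0.245 = 0.48.

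**Step 3: the four readings of the sentence.** Let δ be the true test minus SDF difference, so that positive means the test regimen is worse.

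- A: test minus SDF, lower limit above +0.8. Probability = P(Z > (0.8 + 0.48 − δ)/0.245).
- B: SDF minus test, lower limit above +0.8. Same formula with −δ in place of δ.
- C: SDF minus test, lower limit above −0.8. This is identical to the upper limit of test minus SDF lying below +0.8. Probability = P(Z < (0.8 − 0.48 − δ)/0.245).
- D: test minus SDF, lower limit above −0.8. Probability = P(Z > (−0.8 + 0.48 − δ)/0.245).

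Probability that the criterion is met (normal approximation, 133 per group):

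| Reading | δ = −1.6 | δ = 0 | δ = +0.4 | δ = +0.8 | δ = +1.6 |
|---|---|---|---|---|---|
| A | <0.0001 | 9 × 10⁻⁸ | 0.0002 | 0.025 | 0.90 |
| B | 0.90 | 9 × 10⁻⁸ | <0.0001 | <0.0001 | <0.0001 |
| C | 1.00 | 0.90 | 0.37 | 0.025 | <0.0001 |
| D | <0.0001 | 0.90 | 0.998 | 1.00 | 1.00 |

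**Step 4: what each reading shows.** A is a test that the regimen is worse by more than the margin. B is a test that it is better by more than the margin. Under either, 90% probability is reached only at a true difference of 1.6 surfaces, so the printed +0.8 does not fit 90% power under equality. C is a proper non-inferiority rule: 90% success at equality and 2.5% when the test regimen is worse by exactly 0.8. D also gives 90% at equality, so the sample size alone does not exclude it, but it gives no protection: success becomes more likely as the test regimen gets worse. Only the worded hypothesis rules D out.

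**The case against.** The strongest reply is that margins are often quoted as magnitudes. If 0.8 means −0.8 and the difference is SDF minus test, the sentence in 3.2 is correct as it stands (reading C). The text gives this some support. Section 3.2 names SDF before the test regimen, section 3.4 makes SDF Group 1, and 3.2 speaks of comparing a preventive effect, for which higher is better. The sample size fits reading C. The hypothesis fixes the direction of the claim, so a careful analyst would not declare success on a regimen shown to be worse. The sentence also sits in the sample-size section, and an analysis plan that is not shown may state the operating rule in full.

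Much of this stands. A reader might infer that the rule necessarily points the wrong way, or that the trial would accept a clearly worse regimen. The documents do not support that: it needs both a sign and an order of subtraction that the protocol never gives.

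What the reply does not remove is that reading C needs two unstated choices. Supplying only the minus sign leads to reading D. Nor is this a complaint about detail left to an analysis plan. The protocol chose to state a criterion for its primary hypothesis, and with the margin as printed that criterion is wrong in either order.

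**Conclusion.** The point holds as an error of statement, not as proof of a wrong intention. With the printed +0.8, the criterion in 3.2 shows inferiority or marked superiority and conflicts with the section's own 90% power at 133 per group (about 9 × 10⁻⁸ against 0.90 at equality). It becomes valid only with SDF minus test and a margin of −0.8, neither of which is stated. With −0.8 and test minus SDF it would pass a regimen worse by 0.8 with probability close to 1.

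These figures assume SD 2.0, 133 evaluable elders per group and approximate normality of the difference in means; the comparison with 90% power also assumes a true difference of zero. The sample size is not affected, and the intended rule was probably the valid one. The correction matters because this is the protocol's only non-inferiority criterion for the primary hypothesis.

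**What to change.** In section 3.2, define the difference as mean new carious root surfaces at 24 months, povidone iodine/varnish minus SDF. State that non-inferiority is concluded if the upper limit of the two-sided 95% confidence interval is below +0.8 surface. The mirror form is equivalent: SDF minus povidone iodine/varnish, with the lower limit above −0.8. Choose one form and put the same rule in section 3.5, so that the primary analysis refers to the margin as well as to a t-test for a difference.

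The cost is one sentence in each section. The sample size (133 per group, 332 in total) and the conduct of the trial do not change.

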### **3.3. The baseline and follow-up examinations**

The baseline and follow-up examinations after 12 and 24 months will be carried out in the residential home by a single trained examiner. A portable dental chair, an intra-oral LED light, disposable dental mirrors and CPI probes will be used in the examination.

For each tooth that is not indicated for extraction, status of its crown and its root will be assessed and recorded separately. Caries diagnosis is based on visual and tactile inspection. No radiograph will be taken. Plaque and food debris that obscures visual inspection of the tooth surfaces will be removed. Four surfaces (mesial distal, buccal and lingual) per tooth will be examined and the status will be recorded using the following codes which basically follow the criteria recommended by the International Caries Detection and Assessment System (ICDAS II) Coordinating Committee (2009).

The oral hygiene status of the subject will be assessed and recorded by using the Visible Plaque Index (Ainamo & Bay, 1975). The presence or absence of visible plaque will be recorded on four surfaces (mesial, distal, buccal and lingual) per tooth.

The gingival status of the subject will be assessed and recorded using by the Gingival Bleeding Index (Ainamo & Bay, 1975). The presence or absence of bleeding within 10 seconds after running a probe across the gingival margin will be recorded on four surfaces (mesial, distal, buccal and lingual) per tooth.

Other information that will be recorded included whether the subject normally wears a removable partial denture or not, and the subject's general health status and medications that affect saliva flow rate.

The same examiner will carry out all the baseline and follow-up examinations without knowing the study group assignment of the subjects. It has been shown that good intra-examiner reproducibility can be achieved after training (Tan et al., 2010) and a random sample of 10% of the subjects will be re-examined during each examination to monitor intra-examiner reproducibility.

At the examinations, the subjects will be asked to report on their oral hygiene practices, use of fluoridated toothpaste and other topical fluoride agents, and use of dental services during the study period.

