### **3.5. Statistical analysis**

The collected data will be entered into a computer and analyzed using the software SPSS for Windows version 20. T-test and Chi-square test will be used, as appropriate, to assess the differences in the distribution of age, gender, denture wearing, number of remaining teeth, number of active caries lesions, oral hygiene practice and status, and gingival status at baseline between the two study groups.

The number of root surfaces with new caries found at each follow-up examination will be calculated. Two-sample t-test test will be used to find out if there are statistically significant differences between the two study groups in the number of tooth surfaces that have developed new dental caries. Both intention-to-treat and per protocol analysis will be performed to compare the effectiveness and efficacy of the two study preventive methods.

Two-level, tooth surface and subject, survival analysis will be used to assess the rates of arrest of active root surface caries in the two study groups (Wong et al. 2005). The statistical significance level for all tests will be set at 5%.

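### The caries-arrest hypothesis is worded as non-inferiority, but the stated 85% is the power to show a difference, and the protocol states no arrest margin

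*Protocol*

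**What the plan says.** Protocol, Null hypotheses to be tested, item 2: the test regimen "is at least not appreciably worse than a 38% SDF solution in arresting active root caries over a 24-month period". The form is the same as that of item 1, which the protocol introduces as the hypothesis of a non-inferiority trial.

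Protocol 3.2 (Sample size) sets one margin, for the primary outcome: "A non-inferiority margin of 0.8 surface for the difference in the mean number of new caries surfaces over the 24-month study period". For arrest, it assumes a mean of one lesion per subject, so that "there will be 332 root caries lesions in total or 166 lesions in each study group for caries arrest treatment". It then states that "there is approximately 85% power that an absolute 15% difference in dental caries arrest rates between two groups can be shown" as significant at the 5% level by chi-square test, "when the overall success rate of the caries arrest treatment is around 80" per cent.

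Protocol 3.5 (Statistical analysis): "Two-level, tooth surface and subject, survival analysis will be used to assess the rates of arrest of active root surface caries" in the two groups. The significance level for all tests is 5%. No criterion is given for concluding that arrest is not appreciably worse.

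**The concern.** The protocol sets out to show that arrest under the test regimen is acceptably close to that under silver diammine fluoride, but calculates the power to show that the two differ. These are different tests. A non-inferiority claim needs a margin and a confidence limit that excludes it. A difference test that fails to reach significance excludes nothing in particular.

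Two consequences follow. A reader cannot tell how likely the trial is to support its second hypothesis. And because 5% significance tests are the only stated criterion, a non-significant arrest comparison could be taken as support for that hypothesis even when the data are compatible with a clearly lower arrest rate.

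**Working it through.** **Inputs.** From Protocol 3.2: 166 lesions per group, 15-point difference, two-sided 5% chi-square test, success rate about 80%, dropout 20%. Applying the dropout to lesions gives 166 × 0.8 ≈ 133. That is a low figure for a survival analysis, since subjects lost after the 12-month examination still contribute. Assumptions of this check: lesions are independent; for non-inferiority, both true arrest rates are 80% and the test is one-sided at 2.5%.

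**1. The protocol's own figure.** Difference-test power without continuity correction is Φ[(|p1 − p2| − 1.96·s0)/s1], with s0 = √(2p̄(1 − p̄)/n), s1 = √((p1(1 − p1) + p2(1 − p2))/n) and p̄ the average of p1 and p2.

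For 80% v 65% at n = 166: s0 = 0.0490, s1 = 0.0483, power = Φ[(0.15 − 0.0960)/0.0483] = 86.8%.

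| Rates | n = 166 | n = 133 |
|---|---|---|
| 80% v 65% (one group at 80%) | 86.8% | 78.5% |
| 87.5% v 72.5% (average of both groups 80%) | 93.1% | 86.8% |

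So about 85% is reached in two ways: 80% v 65% before dropout, or an average of 80% after dropout. The figure is not an arithmetic error. Under either reading it is the power of a test of difference.

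**2. Power for the hypothesis as worded.** Non-inferiority power is Φ[M/√(2 × 0.80 × 0.20/n) − 1.96], where M is the margin. The standard error is √(0.32/166) = 0.0439, or √(0.32/133) = 0.0491. For M = 0.10 and n = 166: Φ(0.10/0.0439 − 1.96) = Φ(0.318) = 62%. As the protocol gives no margin, a range is shown:

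| Assumed margin | n = 166 | n = 133 |
|---|---|---|
| 15 points | 93% | 86% |
| 10 points | 62% | 53% |
| 5 points | 21% | 17% |

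The hazard-ratio scale changes little. With examinations at 12 and 24 months and a constant hazard assumed, the same margins correspond to hazard ratios ln(1 − q)/ln(0.20), with q = 0.80 − M: 0.652, 0.748 and 0.861. Power is then 92%/86%, 63%/54% and 22%/18%.

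**3. What a non-significant difference would mean.** The chance of non-significance is 1 − power from step 1:

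| True deficit | Control at 80%: n = 166 / 133 | Average at 80%: n = 166 / 133 |
|---|---|---|
| 10 points | 44% / 53% | 37% / 47% |
| 15 points | 13% / 21% | 7% / 13% |

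As an illustration, suppose the observed rates are 80% and 71% with 166 lesions per group. Then z = 0.09/√(2 × 0.755 × 0.245/166) = 0.09/0.0472 = 1.91, which is not significant. The 95% interval still reaches a deficit of 0.09 + 1.96 × 0.0469 = 0.18, that is 18 points.

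**4. Precision, if the aim is estimation.** The 95% half-width is 1.96·√(0.32·DE/n), where DE is the design effect for several lesions in one subject. With DE = 1 it is 8.6 points (166) or 9.6 (133). With an assumed DE of 1.3 it is 9.8 or 11.0.

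**The case against.** The strongest reply is that the conflict is narrow. Objective 2 only says that the two methods will be compared on arrest, and a difference power and a comparison of arrest rates both fit that. On this view one phrase in the hypothesis is out of line, and the margin and decision rule for a secondary outcome can be left to a statistical analysis plan. This does not remove the point. Objective 1 uses the same neutral verb, and it is the non-inferiority objective, so the verb settles nothing. A margin set in an analysis plan would still not turn the 85% into the power for the second hypothesis. Nor can the 15 points be read as an implied margin, because they are a difference that "can be shown to be statistically significant at the 5% level using Chi-square test".

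Other parts of the reply stand. The protocol nowhere says that a non-significant result will be read as support; that risk is inferred. The error rates are lower if 80% is the average of both groups, and both readings are therefore shown. Clustering is a side issue whose effect depends on the reading: at 166 lesions and a design effect of 1.1 to 1.3, the 86.8% falls to about 83% to 77%, while the 93.1% falls only to about 91% to 85%. Choosing an arrest margin is a clinical judgement and more than a wording change.

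**Conclusion.** The point holds. The second hypothesis claims non-inferiority on arrest, the stated 85% is the power to detect a difference, and nothing in the protocol connects the two. As written, the plan cannot support the second hypothesis. The power to do so could be anywhere from about 17% to 93% over margins of 5 to 15 points, given independent lesions, 133 to 166 per group and equal true arrest rates of 80%. Only those sizes rest on assumptions; the mismatch itself is in the text. The outcome is secondary and the trial's sample size does not depend on it, so this should be corrected but does not threaten the primary comparison.

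**What to change.** Do one of two things.

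(a) Keep the non-inferiority hypothesis. State and justify an arrest margin, either on the scale the two-level survival analysis reports (for example the arrest hazard ratio) or on the 24-month arrest proportion derived from that model. Judge the 95% confidence interval from that analysis against the margin, and replace the 85% with the power of that test.

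(b) Reword the second hypothesis as estimation of the arrest difference, with a 95% confidence interval that allows for several lesions per subject, and make no non-inferiority claim. In place of the power, give the expected half-width: about 9 to 10 points before clustering, or 10 to 11 at an assumed design effect of 1.3.

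Under either option, say which two arrest rates the 80% stands for and how many lesions are expected after dropout.

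Neither option needs more participants; 133 and then 166 per group for the primary outcome are unchanged. Option (b) is a change of wording and costs only a weaker claim. Option (a) needs a clinical justification of the margin and may expose low power, for example 53% to 62% at 10 points.

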## 1. Background

With ageing of the population in most of the economically well-developed areas, tooth decay in the elders has become an important dental public health issue and a heavy burden on the oral health care system. The latest Hong Kong territory-wide oral health survey conducted by the government in 2011 found that 48% of the 65-74 year-old community-dwelling elders had untreated dental caries and 25% of them had root surface caries (Department of Health, 2013). Furthermore, the same survey found that the dental caries situation of the elders who lived in residential care homes or attended long-term care facilities was worse. The institutionalized elders are a high risk group for dental caries in Hong Kong as well as in other countries (Chalmers et al., 2002).

Untreated tooth decay can lead to pain and loss of teeth, and affect general health. Thus, there is an urgent need to develop effective preventive and management measures to improve the dental caries situation among the elders, especially those living in residential care homes. The Hong Kong government financially support non-profit-making non-governmental organizations (NGO) to establish dental outreach teams to provide on-site basic dental care services to the elders who are receiving long-term care. At present, there are around 20 NGO dental outreach teams serving over 30,000 elders in most of the residential care homes throughout Hong Kong. The dental outreach teams, consisting of dentists and dental assistants, bring along hand instruments and portable dental equipment to the residential homes and provide on-site dental examination, oral health education, prevention, scaling and simple dental restorations (Lo et al., 2004). The services of the outreach dental teams follow a general protocol, and are coordinated and monitored by the government Department of Health.

In a recent systematic review by Gluzman and co-workers (2013), eight preventive agents for preventing dental root caries in older adults were identified. In the conclusion, they recommended that the best choice for primary prevention of root caries was annual application of 38% SDF solution while that for secondary prevention of root caries, i.e. arresting active lesions, was professional application of 5% NaF varnish every 3 months.

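### The 85% power stated for caries arrest in 3.2 ignores within-elder clustering and the protocol's own 20% dropout, and needs restating as a conditional range

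*Protocol*

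**What the plan says.** Section 3.2 first sizes the trial on the primary outcome: 133 elders per group, raised to 166. The reason given for the increase is "Allowing for a drop-out rate of 20% in this 24-month study".

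Its second paragraph turns to caries arrest. It takes "an estimated mean number of one untreated early/shallow root caries lesions per subject" and multiplies by 332 elders, so that "there will be 332 root caries lesions in total or 166 lesions in each study group for caries arrest treatment". On that count it states that "there is approximately 85% power that an absolute 15% difference in dental caries arrest rates between two groups can be shown". The figure refers to a chi-square test with a 5% significance level and assumes that about 80% of lesions arrest overall. The paragraph gives no within-elder correlation, no design effect, no distribution of lesions across elders and no reduction for lesions lost to follow-up. It also does not state the two group-specific arrest rates.

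Section 3.5 plans a different analysis for the same outcome: "Two-level, tooth surface and subject, survival analysis will be used to assess the rates of arrest of active root surface caries". A baseline lesion is not among the inclusion criteria in section 3.1. On how lesions are spread, the Background offers one figure, for community-dwelling elders aged 65 to 74: "25% of them had root surface caries".

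**The concern.** A mean of one lesion per elder is not one lesion in each elder. Since elders without lesions can enrol, some will contribute none and others several. Lesions in one mouth share saliva, plaque, diet and treatment, so their outcomes are likely to be correlated. The two-level model in 3.5 allows for this; the power sentence in 3.2 does not.

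The paragraph also treats every baseline lesion as evaluable at 24 months, directly after a paragraph that expects a fifth of elders to be lost.

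The stake is how the secondary result will be read. If arrest rates do not differ significantly, a stated power of about 85% invites the conclusion that a 15-point difference has been ruled out. The design may have had a considerably smaller chance of detecting one.

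**Working it through.** **Inputs from the Protocol.** 166 lesions per group; absolute difference 0.15; overall arrest rate about 0.80; 5% level (taken as two-sided); chi-square test; 20% dropout (all 3.2). Two-level analysis (3.5).

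**Inputs not in the Protocol, assumed.** Within-elder correlation (ICC) 0.1 to 0.3. Size-weighted mean number of lesions per affected elder, m, of 2 or 4.
- m = 2 is what pure chance gives: for Poisson counts with mean 1, E(m²)/E(m) = 2/1 = 2.
- m = 4 spreads a mean of one over the Background's 25% prevalence: 1/0.25 = 4, with equal counts.

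**Formula for independent lesions.** With p̄ the mean of the two rates and d their difference, power = Φ{[d√n − 1.96√(2p̄(1−p̄))] / √(p1(1−p1)+p2(1−p2))}.

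**Step 1: the plan's own figure.**
- Overall 80% taken literally, 0.725 v 0.875, n = 166: [0.15×12.884 − 1.96×0.5657]/0.5557 = 1.48, power **93.1%** (91.0% with continuity correction).
- Same rates, n = 166×0.8 ≈ 133: [0.15×11.533 − 1.96×0.5657]/0.5557 = 1.12, power **86.8%** (83.2% with continuity correction).
- 0.65 v 0.80, n = 166: [0.15×12.884 − 1.96×0.6315]/0.6225 = 1.12, power **86.8%** (83.9% with continuity correction).
- 0.65 v 0.80, n = 133: power **78.5%**, before any clustering.

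So about 85% can be reached, but only by changing either the number of lesions or the meaning of the overall rate from what the sentence says.

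**Step 2: room for clustering.** For 85% power, 0.725 v 0.875 needs 127 independent lesions per group and 0.65 v 0.80 needs 158. The largest tolerable design effect is therefore:
- 166/127 = 1.31 (literal rates, no loss);
- 133/127 = 1.05 (literal rates, 20% loss);
- 166/158 = 1.05 (65% v 80%, no loss).

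**Step 3: power with clustering.** Design effect DE = 1 + (m−1)×ICC; effective n = n/DE; rates 0.725 v 0.875. The last column solves the same formula for d with the rates centred on 80%.

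| m | ICC | DE | 133/DE | Power, 133 lesions | Power, 166 lesions | Difference giving 85% power, 133 lesions |
|---|---|---|---|---|---|---|
| 2 | 0.1 | 1.1 | 120.9 | 83.5% | 90.7% | 15.3 points |
| 2 | 0.2 | 1.2 | 110.8 | 80.1% | 88.1% | 16.0 points |
| 2 | 0.3 | 1.3 | 102.3 | 76.9% | 85.4% | 16.6 points |
| 4 | 0.1 | 1.3 | 102.3 | 76.9% | 85.4% | 16.6 points |
| 4 | 0.2 | 1.6 | 83.1 | 67.9% | 77.5% | 18.4 points |
| 4 | 0.3 | 1.9 | 70.0 | 60.4% | 70.1% | 20.0 points |

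**The case against.** A reader might infer that treating lesions as independent is by itself enough to take the design below 85%. The document does not support that. On the literal inputs, unclustered power is 93%, and clustering alone keeps it at 85% up to a design effect of about 1.31. That covers the whole m = 2 scenario. The shortfall in the table depends on dropout as well, and dropout uses up most of the headroom before any correlation enters.

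A reader might also infer an arithmetic error. That is not shown either. Two plausible readings give about 87%, so the figure is ambiguous about its inputs.

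Other fair points:
- The correlation and the lesion distribution come from outside the document. The m = 4 case borrows a prevalence from community-dwelling elders, and the Background says that elders in long-term care are worse off. Lesions may therefore be spread over more elders, which makes m = 4 an upper scenario. It is not a strict bound, since unequal counts would push m up.
- The mildest case, 83.5%, hardly differs from approximately 85%.
- Removing 20% of lesions outright is somewhat severe: an elder lost after the 12-month examination still contributes to a survival analysis.
- The design-effect formula concerns a binary endpoint and only approximates the two-level survival model.
- Section 2 words the secondary hypothesis as non-inferiority, whereas 3.2 powers a test of difference. The recalculation keeps the framing of 3.2 and says nothing about power for non-inferiority.

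All of this stands, and it makes the conclusion conditional. It does not rescue the sentence: the only reading with real headroom assumes that no lesion is lost, against the dropout planned in the same section.

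**Conclusion.** The concern holds in conditional form. The stated 85% belongs to a chi-square test on independent lesions with no loss, which is neither the planned analysis nor the planned follow-up, and the sentence's literal inputs give 93%. The two readings that come near 85% leave room for only about 5% inflation in variance; at m = 2, a correlation above about 0.05 exceeds that.

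Under 20% loss, 72.5% v 87.5% and correlations of 0.1 to 0.3, power for a 15-point difference is about 60% to 84%. A shortfall from 85% is therefore likely but not certain, and its size cannot be fixed from the document. The point affects one secondary power statement. The primary sample size is untouched, and the planned analysis of arrest already handles the clustering.

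**What to change.** In 3.2, replace the sentence on arrest power and delete the claim resting on 332 independent lesions. The new text should state:
- the two assumed arrest rates, not only an overall rate;
- the evaluable lesions per group after 20% loss (about 133 if the mean of one per elder holds);
- the assumed distribution of lesions across elders and the within-elder correlation, with their source;
- the resulting power as a range, described as an approximation to the two-level analysis in 3.5.

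Under the assumptions used here, the range would be about 60% to 84% for a 15-point difference, with 85% reached only for differences of roughly 15 to 20 points (15.3 at a design effect of 1.1, 20.0 at 1.9). If the sponsor holds a correlation and lesion counts from its earlier trial in residential homes, those should replace the assumed values.

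The cost is one rewritten statement. Enrolment and analysis do not change; the secondary power figure becomes less favourable.
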